#### Follow-Up Reports

The Investigator must continue to follow the patient until the SAE has subsided or until the condition becomes chronic in nature, stabilizes (in the case of persistent impairment), or the patient dies.

Within 24 hours of receipt of follow-up information, the Investigator must update the SAE form electronically in the EDC system for the study and submit any supporting documentation (eg, patient discharge summary or autopsy reports) to Medpace Clinical Safety via fax or email. If it is not possible to access the EDC system, refer to the procedures outlined above for initial reporting of SAEs.

#### 8.4 **Pregnancy Reporting**

If a patient becomes pregnant during the study or within the safety follow-up period defined in the protocol, the Investigator is to stop dosing with study drug(s) immediately and the patient should be withdrawn from the study. Early termination procedures should be implemented at that time.

A pregnancy is not considered to be an adverse event or SAE; however, it must be reported to Medpace Clinical Safety within 24 hours of knowledge of the event. Medpace Clinical Safety will then provide the Investigator/site the Exposure In Utero (EIU) form for completion. The Investigator/site must complete the EIU form and fax/email it back to Medpace Clinical Safety.

If the female partner of a male patient becomes pregnant while the patient is receiving study drug or within the safety follow-up period defined in the protocol, the Investigator should notify Medpace Clinical Safety as described above.

The pregnancy should be followed until the outcome of the pregnancy, whenever possible. Once the outcome of the pregnancy is known, the EIU form should be completed and faxed/emailed to Medpace Clinical Safety. If the outcome of the pregnancy meets the criteria for immediate classification as an SAE (ie, postpartum complication, spontaneous abortion, stillbirth, neonatal death, or congenital anomaly), the Investigator should follow the procedures for reporting an SAE.

# 8.5 Expedited Reporting

The Sponsor/designee will report all relevant information about Suspected Unexpected Serious Adverse Reactions (SUSAR) that are fatal or life-threatening as soon as possible to the Food and Drug Administration (FDA), applicable competent authorities in all the Member States concerned, and to the Central Ethics Committee, and in any case no later than 7 days after knowledge by the Sponsor/designee of such a case. Relevant follow-up information will subsequently be communicated within an additional 8 days.

All other SUSARs will be reported to the FDA, applicable competent authorities concerned, and to the Central Ethics Committee concerned as soon as possible but within a maximum of 15 days of first knowledge by the Sponsor/designee.

The Sponsor/designee will also report any additional expedited safety reports required in accordance with the timelines outlined in country-specific legislation.

The Sponsor/designee will also inform all Investigators as required per local regulation.

The requirements above refer to the requirements relating to APX001.

#### 8.6 Special Situation Reports

Special situation reports include reports of overdose, misuse, abuse, medication error, and reports of adverse reactions associated with product complaints.

- **Overdose:** Refers to the administration of a quantity of a study drug given per administration or cumulatively (accidentally or intentionally), which is above the maximum recommended dose according to the protocol. Clinical judgment should always be applied. In cases of a discrepancy in the drug accountability, overdose will be established only when it is clear that the patient has taken additional dose(s) or the Investigator has reason to suspect that the patient has taken additional dose(s).
- **Misuse:** Refers to situations where the study drug is intentionally and inappropriately used not in a way that is not in accordance with the protocol instructions or local prescribing information and may be accompanied by harmful physical and/or psychological effects.
- Abuse: Is defined as persistent or sporadic, intentional excessive use of a study drug, which is accompanied by harmful physical or psychological effects.
- **Medication error:** Is any unintentional error in the prescribing, dispensing, or administration of a study drug by a healthcare professional, patient, or consumer, respectively. The administration or consumption of the unassigned treatment and administration of an expired product are always reportable as medication errors, cases of patients missing doses of study drug are not considered reportable as medication error.
- **Product complaint:** Is defined as any written, electronic, or oral communication that alleges deficiencies related to the identity, quality, durability, reliability, safety, effectiveness, or performance of a drug or device after it is released for distribution. A special situations form will only be completed if a complaint is associated with an adverse drug reaction.

All special situation events as described above must be reported on the Special Situations Report form and faxed/emailed to Medpace Clinical Safety (contact information listed below) within 24 hours of knowledge of the event. All adverse events associated with these Special Situation reports should be reported as adverse events or SAEs as well as recorded on the adverse event eCRF and/or the SAE report form. Details of the symptoms and signs, clinical management, and outcome should be provided, when available.

#### 8.7 Clinical Laboratory Evaluations

Screening laboratory assessments to determine eligibility will be performed at the local laboratory and may have been collected as SOC within the previous 24 hours. Laboratory assessments collected after Screening will be sent to the central laboratory for analysis.

Clinical laboratory assessments (serum chemistry, hematology [including CBC with differential], coagulation [including PT/INR], and urinalysis) will occur at Screening; predose on Days 1 (Baseline), 7, 14, 28, and 42; at EOST; and at the E/T Visit (if applicable).

A urine or serum pregnancy test will be performed at Screening; on Days 1 (Baseline) (if the Screening Visit occurred  $\geq$ 96 hours prior to Day 1 [Baseline]), 28, and 42; at EOST; at the Follow-Up Visit; and at the E/T Visit (if applicable) for all women of childbearing potential.

If clinically indicated and at the discretion of the Investigator, or if a suspected adverse event is identified, clinical laboratory assessments may be conducted at any time during the study and compared to Baseline. See APPENDIX E for a complete list of clinical laboratory analytes.

#### 8.8 Vital Signs

Vital signs will include temperature, blood pressure, heart rate, respiratory rate, and oxygen saturation and will be collected at Screening; predose on Days 1 (Baseline), 7, 14, 21, 28, 35, and 42; at EOST; at the Follow-Up Visit; and at the E/T Visit (if applicable). Patients should be supine for at least 5 minutes prior to measurement of vital signs.

#### 8.9 Electrocardiograms

A 12-lead ECG will be obtained in triplicate at Screening, Days 3, 7, 14 and 42, EOST, and the E/T Visit (if applicable). Patients should be supine for at least 5 minutes prior to the collection of 12-lead ECGs.

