#### 6.3.1 Day 1 (Baseline)

The following procedures will be performed on Day 1 (Baseline):

- Perform urine or serum pregnancy test on women of childbearing potential only if the Screening Visit occurred ≥96 hours prior to Day 1 (Baseline).
- Perform a neurological examination (all patients) and a symptom-directed physical examination as clinically indicated (ie, new signs or symptoms and follow-up on earlier findings) and measure weight.
- Assess clinical signs and symptoms.
- Record vital signs, including temperature, blood pressure, heart rate, respiratory rate, and oxygen saturation.
- Perform clinical laboratory assessments (serum chemistry, hematology [including CBC with differential], coagulation [including PT/INR], and urinalysis).
- Collect serum samples for analysis of CCI and C predose.
- Collect samples for fungal cultures (eg, from BAL fluid, sputum, bronchial brush, sinus aspirate, tracheal aspirate) as clinically indicated.
- Collect BAL samples per SOC for culture and CCI testing as clinically indicated.
- Administer a loading dose of 1000 mg APX001 by IV infusion over 3 hours BID within the first 24 hours after initiation of the first infusion.
- Collect plasma PK samples predose and 3 hours post start of infusion.
- Record concomitant medications.
- Assess adverse events.

# 6.3.2 Day 2

The following procedures will be performed on Day 2:

- Assess clinical signs and symptoms.
- Collect serum sample for analysis of CCI predose.

- Collect samples for fungal cultures (eg, from BAL fluid, sputum, bronchial brush, sinus aspirate, tracheal aspirate) as clinically indicated.
- Collect BAL samples per SOC for culture and CCI testing as clinically indicated.
- Administer 600 mg APX001 by IV infusion over 3 hours QD.
- Collect plasma PK samples predose and 3 hours post start of infusion.
- Record concomitant medications.
- Assess adverse events.
- Review accountability for all returned study drug.

# 6.3.3 Day 3

The following procedures will be performed on Day 3:

- Assess clinical signs and symptoms.
- Perform 12-lead ECG in triplicate.
- Collect serum sample for analysis of CCI predose.
- Collect samples for fungal cultures (eg, from BAL fluid, sputum, bronchial brush, sinus aspirate, tracheal aspirate) as clinically indicated.
- Collect BAL samples per SOC for culture and CCI testing as clinically indicated.

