# 6.3.9 Day 42 (± Days)

If EOST procedures are performed after Day 39, Day 42 procedures will not be required. The following procedures will be performed on Day 42 ( $\pm 2$  days):

- Administer 600 mg APX001 by IV infusion over 3 hours QD or 800 mg APX001 PO QD.
- Record Investigator assessment of global response.
- Assess survival status.
- Perform urine or serum pregnancy test on women of childbearing potential only.
- Perform a complete physical examination including assessment of general appearance, skin, eyes, heart, chest, abdomen, and a neurological examination and measure weight.

- Assess clinical signs and symptoms.
- Record vital signs, including temperature, blood pressure, heart rate, respiratory rate, and oxygen saturation.
- Perform 12-lead ECG in triplicate.
- Perform clinical laboratory assessments (serum chemistry, hematology [including CBC with differential], coagulation [including PT/INR], and urinalysis).
- Perform CT scan if clinically indicated.
- Collect serum samples for analysis of CCI and C.
- Collect samples for fungal cultures (eg, from BAL fluid, sputum, bronchial brush, sinus aspirate, tracheal aspirate) as clinically indicated.
- Collect BAL samples per SOC for culture and CCI testing as clinically indicated.
- Collect plasma PK samples predose for IV dosing or at any time in clinic for PO dosing.
- Record concomitant medications.
- Assess adverse events.
- Review accountability for all returned study drug.

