#### 7.6 Pharmacokinetic Assessments

Plasma samples for PK (APX001 [prodrug] and APX001A [active moiety]) will be collected predose and 3 hours post start of infusion on Days 1 (Baseline), 2, 3, 7, and 14; predose on Days 28 and 42; and at any time in clinic at EOST, the Follow-Up Visit, and the E/T Visit (if applicable). Additionally, for patients who switch to PO dosing, samples should be collected predose and at 3 hours postdose on the initial day of PO dosing, Day 7, and Day 14 and at any time in clinic on Days 28 and 42, at EOST, at the Follow-Up Visit, and at the E/T Visit (if applicable). If the patient switches back to IV dosing, PK samples should be collected predose and at 3 hours post start of infusion on that day as well.

Optionally, if body fluids are sampled as part of routine patient management (eg, BAL, lumbar puncture, paracentesis, vitreal fluid collection, abscess drainage), within approximately 2 hours of blood sampling for PK, these samples may be stored for future analysis of APX001 and APX001A levels.

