- with the signs include temperature, blood pressure, heart rate, respiratory rate, and oxygen saturation. Measure vital signs at Screening; at predose on Days 1 (Baseline), 7, 14, 21, 28, 35, and 42; at EOST; at the Follow-up Visit; and at the E/T Visit (if applicable). Patients should be supine for at least 5 minutes prior to measurement of vital signs.
- n. Collect 12-lead ECGs in triplicate at Screening, on Days 3, 7, 14 and 42, at EOST, and at the E/T Visit (if applicable). Patients should be supine for at least 5 minutes prior to collection of 12-lead ECGs.
- o. Clinical laboratory assessments include serum chemistry, hematology (including CBC with differential), coagulation (including PT/INR), and urinalysis. Collect blood and urine specimens at Screening; at predose on Days 1 (Baseline), 7, 14, 28, and 42; at EOST; and at the E/T Visit (if applicable).
- p. Clinical laboratory assessments performed at Screening to determine eligibility will be performed at the local laboratory and may have been collected as SOC within the previous 24 hours. Laboratory assessments collected after Screening will be sent to the central laboratory for analysis.
- q. Collect blood samples (serum and plasma) and other diagnostic specimens (eg, BAL) for pathogen DNA analysis utilizing next-generation sequencing (optional), PCR analysis, and collect urine sample for MycoMEIA.
- r. The same CT scanner and imaging protocol used at Screening should be used for subsequent CT scans, if possible. Additional CT scans may be performed during treatment and follow-up if clinically indicated.
- s. Standard of care scans within 3 days of Screening will be accepted as long as the scans can be provided to the central reader.
- t. Perform CT scan if clinically indicated.
- u. Collect serum samples for analysis of CCI at Screening; predose on Days 1 (Baseline), 2, and 3; on Days 7, 14, 28, and 42; at EOST; and at the E/T Visit (if applicable). Analysis of CCI will be reported at the local laboratory and an aliquot of the sample will be sent to the central laboratory for analysis.

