3.10. Electrocardiograms

A 12 lead ECG will be obtained in triplicate at Screening, Days 3, 7, 14 and 42, EOST, and the E/T Visit (if applicable).

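### ECGs on Days 3, 7 and 14 have no set time relative to dose, so a compliant site could record none near the end of infusion; pairing them with the existing 3-hour PK draw is a cheap improvement

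*Protocol*

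**What the plan says.** Protocol section 8.9 schedules the ECGs by day: "A 12-lead ECG will be obtained in triplicate at Screening, Days 3, 7, 14 and 42, EOST", plus the early termination visit. Its only other condition is five minutes supine beforehand. Appendix A note n repeats this: "Collect 12-lead ECGs in triplicate at Screening, on Days 3, 7, 14 and 42, at EOST". The Day 3 visit list (section 6.3.3) says only "Perform 12-lead ECG in triplicate", and the other visit lists are no more specific. SAP section 3.10 carries the same schedule: "A 12 lead ECG will be obtained in triplicate at Screening, Days 3, 7, 14 and 42, EOST, and the E/T Visit (if applicable".

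The neighbouring assessments are timed. Sections 8.7 and 8.8 put on-treatment laboratory tests and vital signs before the dose. Section 7.6 takes plasma for PK "predose and 3 hours post start of infusion on Days 1 (Baseline), 2, 3, 7, and 14; predose on Days 28 and 42". Patients on oral drug have predose and 3-hour postdose samples on Days 7 and 14. Section 5.5.3 gives each IV dose over 3 hours, so on IV days the 3-hour sample falls at the end of infusion.

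SAP section 6.8.11 averages the triplicate at each scheduled visit and summarises values and changes from baseline. It uses neither time from dose nor concentration.

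**The concern.** Safety is part of the primary objective (section 2.1), and ECG intervals are among the planned safety analyses (section 9.2.2). The protocol itself allows that exposure may matter for safety: section 5.6.1.1 warns that several strong CYP inhibitors together may raise levels of the active moiety and affect risk. Section 1 reports that plasma concentrations depend on hematocrit.

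If the ECG can be taken at any hour, the Day 3, 7 and 14 summaries average over patients measured at differing and unstated points of the dosing interval. An effect that follows concentration would be diluted. If ECGs happened to be taken mainly before dosing, it could be missed. The time is chosen at the site, so a near-peak ECG that was never recorded cannot be recovered in analysis.

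**Working it through.** The plan states no figure on this point, so there is none to reproduce. The check has three steps.

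**1. Is an ECG time given anywhere?** The places read were protocol sections 6.3.3 to 6.3.5, 6.3.9, 6.4, 6.7 and 8.9, the Appendix A grid and note n, and SAP sections 3.10 and 6.8.11. None gives a time relative to dose.

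The order of items in the visit lists does not supply one. On Days 3, 7 and 14 the ECG line stands above the dosing line, but the PK line, which includes a predose sample, stands below it. In the Day 42 list (section 6.3.9) dosing comes first and the laboratory tests, which section 8.7 sets predose, come later. The lists are therefore not in time order.

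**2. On which ECG days is there a 3-hour PK sample?**
- On-treatment ECG days: 3, 7, 14, 42.
- Scheduled days with a 3-hour sample on IV dosing: 1, 2, 3, 7, 14.
- Overlap: 3, 7 and 14, that is 3 of the 4 on-treatment ECG days.

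Day 42 drops out: "Collect plasma PK samples predose for IV dosing or at any time in clinic for PO dosing". At EOST, up to 2 days after the last dose (section 6.4), PK is drawn at any time in clinic.

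**3. How much lower could the concentration be at a predose ECG?** The documents give no half-life, so this step is illustrative. Assume one-compartment first-order decline, a 3-hour infusion and a 24-hour interval. The next predose point is 24 − 3 = 21 hours after the end of infusion, so

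trough / end of infusion = 0.5^(21 / t½).

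| Assumed half-life (h) | 21 / t½ | Trough as share of end of infusion |
|---|---|---|
| 12 | 1.750 | 30% |
| 24 | 0.875 | 55% |
| 48 | 0.438 | 74% |
| 72 | 0.292 | 82% |

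Widening the range to 6 and 96 hours gives 9% and 86%. The ratio compares a trough with the end of the preceding infusion. Reading it as predose against end of infusion on the same day also assumes steady state. It applies to IV dosing only.

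**The case against.** **No evidence that ECGs will cluster at trough.** A reader might infer that many will be done with the predose procedures. The documents do not support that. No vital signs or laboratory tests are scheduled on Day 3, and the visit lists are not chronological. What stands is that predose ECGs throughout would be compliant, not that they are likely.

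**Linkage to exposure is not ruled out.** A reader might infer that ECGs can never be related to concentration. If clock times are captured, the planned population PK analysis (section 9.2.2.1) could estimate the concentration at the time of the ECG. The case report form is not among the documents, so whether it captures the time is unknown. This objection stands. It does not restore a near-peak measurement that nobody took.

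**The loss may be modest.** The loading dose is 2 × 1000 = 2000 mg against 600 mg daily. If that load were meant to reach steady state at once (an assumption, not a statement in the plan), the accumulation ratio would be 2000 / 600 = 3.33. The fraction remaining after 24 hours would be 1 − 1/3.33 = 0.70, the half-life about 47 hours, and the trough 0.70^(21/24) = 73% of the end-of-infusion level. This is a fair hint, but no more than that.

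**Three hours is not shown to be peak for oral drug.** Patients may switch from Day 4, and no oral time to peak is given. Nor do the documents show that any ECG effect would follow plasma concentration without delay. Both points stand.

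**The prior for an ECG effect is low and the setting is descriptive.** Section 1 reports no ECG result meeting the criteria for an adverse event in three healthy-volunteer studies, section 1.2.1 lists no cardiac risk, and there is no concentration-ECG objective. This limits the weight of the point. It does not make untimed ECGs informative in sicker patients on many other drugs.

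**Conclusion.** The point holds as a gap in assessment timing. No ECG time relative to dose is stated, and no recording of that time is required, in protocol section 8.9, Appendix A note n or the SAP. On Days 3, 7 and 14 a fully compliant site could take every ECG at or near trough, and the by-visit summary would then mix unknown times from dose.

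The size cannot be determined from the documents. The range of about 30% to 82% rests on assumed half-lives of 12 to 72 hours and one-compartment decline after IV dosing. At its upper end the dilution is modest. It should not be read as an estimate of what this trial would lose, nor as evidence that an ECG effect exists.

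The finding is confined to Days 3, 7 and 14. It contradicts nothing else in the plan and affects no efficacy conclusion. It is worth acting on because the remedy uses a 3-hour attendance that is already scheduled.

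**What to change.** In section 8.9 and Appendix A note n, state that the triplicate ECGs on Days 3, 7 and 14 are taken immediately before the 3-hour PK draw: at the end of infusion for IV dosing, and 3 hours postdose for oral dosing. For oral dosing the gain is pairing with a measured concentration, since that time is not shown to be peak. Require the clock times of the ECG and of the dose to be recorded. SAP section 3.10 should carry the same timing.

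This adds no ECGs and no blood samples and leaves dosing unchanged. The cost is some site scheduling on three visits. Day 42 and EOST are left out because they have no 3-hour IV PK sample; pairing on Day 42 would need an extra draw.

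One limitation remains. No ECG is scheduled on Day 1, so baseline is normally the Screening ECG from Day -5 to -1, at an unstated hour. Change from baseline will still not be matched for time of day.

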#### 8.10 Physical Examinations

A complete physical examination will be conducted at Screening, Day 42, EOST, and the E/T Visit (if applicable). A complete physical examination will include an assessment of general appearance, skin, eyes, heart, chest, abdomen, and a neurological examination. Components of the neurological examination include cranial nerve, sensory, and motor examination; reflex and gait testing; and coordination assessment. Height will be measured at Screening and weight will be measured at Screening; on Days 1 (Baseline), 7, 14, 21, 28, 35, and 42; at EOST; at the Follow-Up Visit; and at the E/T Visit (if applicable).

A neurological examination (all patients) and a symptom-directed physical examination will be conducted as clinically indicated (ie, new signs or symptoms and follow-up on earlier findings) on Days 1 (Baseline), 7, 14, 21, 28, 35, and at the Follow-Up Visit.

# 8.11 Computed Tomography

Computed tomography scans of the chest, sinuses, and/or abdomen will be performed during Screening (SOC scans within 3 days of Screening will be accepted as long as the scans can be provided to the central reader). Repeat CT scans will be performed on Day 14 and at EOST, and if clinically indicated on Days 7, 21, 28, 35, and 42; at the Follow-Up Visit; and at the E/T Visit (if applicable).

The same CT scanner and imaging protocol used at Screening should be used for subsequent CT scans, if possible. Additional CT scans may be performed during treatment and follow-up if clinically indicated.

